3.11 Subgroup Analyses

 Summary statistics and the ANCOVA analysis for htTKV described in Section 3.9.2 will be performed for each of the Mayo Classification groups (ie, Class 1A, 1B, 1C, 1D, and 1E). This will be done for the Month 12, 18, 24, and 30 days post-dose treatment visits.

The formulas for the Mayo classification groups are derived from the methods in Irazabel $(2015)^2$ and are presented in Section 3.15.

• Summary statistics and the ANCOVA analysis for eGFR described in Section 3.9.3 will be performed for each of the Mayo Classification groups (ie, Class 1A, 1B, 1C, 1D, and 1E). This will be done for the Month 12, 18, 24, and 30 days post-dose treatment visits.

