4. STUDY POPULATION

4.1. Inclusion Criteria

Subjects will be included in the study if they meet all of the following inclusion criteria:

- 1. Confirmed diagnosis of ADPKD based on Ravine's criteria. Subjects < 30 years of age must have at least 2 cysts (unilateral or bilateral) while subjects ≥ 30 years of age must have at least 2 cysts in each kidney (ie, total ≥ 4 cysts).
- 2. Cysts must be at least 1 cm in size to be considered.
- 3. At least 18 years old and no more than 60 years old at the time of consent.
- 4. eGFR ≥ 25 mL/min/1.73 m² and ≤ 90 mL/min/1.73 m², using the Modification of Diet in Renal Disease-4 variable formula.
- 5. htTKV must meet the following criteria (htTKV is calculated using total kidney volume obtained from MRI divided by height in meters):
 - \geq 500 mL for subjects 18-35 years of age
 - > 750 mL for subjects 36-49 years of age
 - > 900 mL for subjects 50-60 years of age
- 6. Subject has the following laboratory values:
 - Platelets > lower limit of normal (LLN)
 - Hemoglobin > 9 g/dL
 - Total bilirubin $\leq 1.5 \text{ mg/dL}$
 - Aspartate aminotransferase < 2.5 × ULN
 - Alanine aminotransferase $< 2.5 \times ULN$
 - Prothrombin time/partial thromboplastin time $\leq 1.5 \times ULN$
 - International normalized ratio (INR) \leq 1.5, except those subjects taking warfarin who must have INR \leq 3
 - Albumin > LLN
 - Amylase $\leq 1.5 \text{ x ULN}$
 - Lipase $< 1.5 \times ULN$
 - Serum potassium within normal limits
 - Serum magnesium within normal limits
- 7. Female subjects of childbearing potential must have a negative pregnancy test at screening. Females of childbearing potential are defined as sexually mature women without prior hysterectomy, bilateral tubal ligation, or who have had any evidence of menses in the past 12 months. However, women who have been amenorrheic for 12 or

more months are still considered to be of child bearing potential if the amenorrhea is possibly due to prior chemotherapy, anti-estrogens, or ovarian suppression.

- Women of childbearing potential must have a negative urine pregnancy test (positive urine tests are to be confirmed by serum test) documented within the 24-hour period prior to the first dose of study drug.

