3.15 Mayo Classification Formula

Table 3 lists the Mayo Classifications (ie, 1A, 1B, 1C, 1D, and 1E) htTKV criteria for a given age as presented in Irazabel (2015)²; supplemental Table S2.

For classes 1A, 1B, 1C, and 1D the upper limits of htTKV are presented, for class 1E, the minimal value is presented (ie, as such the values in Table 3 for the 1D and 1E columns are equivalent).

For example, a 40 year old with an htTKV of 650 would have a classification of 1C.

Figure 1 provides an illustration of the Mayo Classification categories, as copied from "Figure 3" of Irazabel (2015)².

Age (years)	1A*	1B*	1C*	1D*	1E [†]
15	188	234	290	359	359
16	190	241	303	381	381
17	193	248	317	404	404
18	196	255	331	428	428
19	199	263	346	454	454
20	202	271	362	481	481
21	205	279	378	510	510
22	208	287	395	541	541
23	211	296	413	573	573
24	214	305	431	607	607
25	218	314	451	644	644
26	221	323	471	682	682
27	224	333	492	723	723
28	228	343	514	767	767
29	231	353	538	813	813
30	234	364	562	862	862
31	238	375	587	913	913
32	242	386	613	968	968
33	245	398	641	1026	1026
34	249	410	670	1088	1088
35	253	422	700	1153	1153
36	256	435	732	1222	1222
37	260	448	765	1295	1295

Table 3: Mayo Classification HtTKV Limits for Age

38	264	461	799	1373	1373
39	268	475	835	1456	1456
40	272	489	872	1543	1543
41	276	504	912	1635	1635
42	280	519	953	1734	1734
43	285	535	996	1838	1838
44	289	551	1040	1948	1948
45	293	567	1087	2065	2065
46	298	584	1136	2189	2189
47	302	602	1187	2320	2320
48	307	620	1241	2459	2459
49	311	638	1297	2607	2607
50	316	658	1355	2763	2763
51	321	677	1416	2929	2929
52	325	698	1480	3105	3105
53	330	719	1546	3291	3291
54	335	740	1616	3488	3488
55	340	762	1688	3698	3698
56	345	785	1764	3919	3919
57	350	809	1844	4155	4155
58	356	833	1927	4404	4404
59	361	858	2014	4668	4668
60	366	884	2104	4948	4948
61	372	910	2199	5245	5245
62	378	938	2298	5560	5560
63	383	966	2401	5893	5893
64	389	995	2509	6247	6247
65	395	1024	2622	6622	6622
66	401	1055	2740	7019	7019
67	407	1087	2863	7440	7440
68	413	1119	2992	7887	7887
69	419	1153	3127	8360	8360
70	425	1188	3268	8861	8861
71	432	1223	3415	9393	9393
72	438	1260	3568	9957	9957
73	445	1298	3729	10554	10554
74	451	1337	3897	11187	11187
75	458	1377	4072	11859	11859
76	465	1418	4255	12570	12570
77	472	1461	4447	13324	13324
78	479	1505	4647	14124	14124
79	486	1550	4856	14971	14971

[†]Minimal values shown for Class 1E

Figure 1: Illustration of Mayo Classification

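### The Mayo-class subgroup plan models two classes that eligibility leaves essentially empty and has no test of whether the effect differs by class

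*SAP*

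**What the plan says.** SAP 3.11 asks for summary statistics and an ANCOVA "for each of the Mayo Classification groups (ie, Class 1A, 1B, 1C, 1D, and 1E". It does so once for htTKV and once for eGFR, and for each it adds: "This will be done for the Month 12, 18, 24, and 30 days post-dose treatment visits". The htTKV model is that of SAP 3.9.2 (treatment, baseline log10 htTKV). The eGFR model is that of SAP 3.9.3 (treatment, baseline eGFR, age, baseline htTKV). Neither has a class term or a treatment-by-class term. The only interaction in the SAP is treatment-by-time in the longitudinal model of 3.10.1. No minimum class size or pooling rule is given.

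Class is read from SAP Table 3 (section 3.15), by age and htTKV: "For classes 1A, 1B, 1C, and 1D the upper limits of htTKV are presented".

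Inclusion criterion 5 in Protocol 4.1 sets a lower limit on htTKV in three age bands: "500 mL for subjects 18-35 years of age", "> 750 mL for subjects 36-49 years of age" and "> 900 mL for subjects 50-60 years of age". The synopsis and the body differ on whether exactly 500 mL qualifies in the youngest band, which changes nothing here. Protocol section 3 bases entry on local MRI readings and has central readings made at baseline and during the study.

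**The concern.** The subgroup plan lists all five classes, although the trial enriches for large kidneys with age-dependent limits. If those limits sit above the 1B limit, two of the five planned fits have nobody to analyse, and the subjects fall into three classes.

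A subgroup analysis by a prognostic class is useful mainly for judging whether the effect depends on class. Separate fits do not address that. In a trial sized for one overall comparison, each class is small and its p-value is largely a matter of chance. A drug with the same effect everywhere can then look as if it works in one class and not in another, and the planned output offers no direct estimate of the difference between classes to correct that impression. Mayo class is the only subgroup factor in the SAP, so this table is where readers will look.

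**Working it through.** **1. The plan's own power figure.** Inputs from SAP 3.1.2: mean changes 83.6 and 26.4 mL, SD 90.0, 40 per group, 2-sided 0.05. The difference is 83.6 − 26.4 = 57.2 mL. The noncentrality is 57.2 / (90 × √(2/40)) = 2.84 on 78 df, giving power of 80.2%. The stated figure of about 80% is reproduced.

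**2. Entry limits against SAP Table 3.** The 1B limit rises with age, so the oldest age in each band is the closest call. For example, the rows at 35 and 49 read "35 253 422 700 1153 1153" and "49 311 638 1297 2607 2607".

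| Age | Entry limit | 1A upper | 1B upper | Drop from entry limit to 1B |
|---|---|---|---|---|
| 35 | 500 | 253 | 422 | 78/500 = 15.6% |
| 49 | 750 | 311 | 638 | 112/750 = 14.9% |
| 58 | 900 | 356 | 833 | 67/900 = 7.4% |
| 59 | 900 | 361 | 858 | 42/900 = 4.7% |
| 60 | 900 | 366 | 884 | 16/900 = 1.8% |

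At none of the 43 ages from 18 to 60 does the 1B limit reach the entry limit. A 1B subject needs a central reading below the local one by the last column or more, which is plausible only near ages 58 to 60. The SAP does not say which age assigns class; at 61 the 1B limit is 910 mL, so a subject who consents at 60 and is classed at 61 could also just qualify. Class 1A would need a central reading about half the local one: (500 − 253)/500 = 49% at age 35, and more at 49 and 60. In addition, an eligible volume cannot be 1C at ages 18–27 or 36, nor 1D at 18–20.

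**3. Number of fits.** Planned: 5 classes × 4 visits × 2 outcomes = 40. In 1C–1E: 3 × 4 × 2 = 24. The other 16 have essentially no data.

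**4. Separate tests under a uniform effect.** The documents give no class distribution, so class sizes are assumed. With 13 per arm in each of three classes, the noncentrality is 57.2 / (90 × √(2/13)) = 1.62 on 24 df, giving power of 34.3%. The classes contain different subjects, so the separate tests are independent:

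P(some significant, some not) = 1 − 0.343³ − 0.657³ = 1 − 0.040 − 0.284 = 0.68.

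Uneven splits give a similar answer. With 20/14/6 per arm (power 50%, 37%, 17%) the result is about 71%. With 24/12/4 (58%, 32%, 12%) it is about 72%.

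**5. Power of the interaction test (2 df).** Noncentral F with λ = Σ wₖ(δₖ − δ̄)², where wₖ = nₖ/(2 × 90²) and δ̄ is the weighted mean effect. With 13 per arm, w = 0.000802. If one class has no effect, λ = 0.000802 × 2181 = 1.75. For a gradient, λ = 0.000802 × 6544 = 5.25. Both have 72 error df.

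| Per-arm split | Two classes at 57.2 mL, one (the smallest if uneven) at 0 | Gradient 0 / 57.2 / 114.4 mL |
|---|---|---|
| 13/13/13 | 20% | 51% |
| 20/14/6 | 13% | 42% |
| 24/12/4 | 11% | 37% |

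**6. What a common error variance could do.** Suppose residual SDs in ratio 1:1:2 with equal class sizes (an illustration; the documents give no class variances). The pooled variance is (1 + 1 + 4)/3 = 2. In the most variable class the standard error is too small by √2/2 = 0.71, so a nominal cut-off of 1.99 acts as 1.41. That is a Type I error of about 16% instead of 5%; in the other two classes it falls below 1%.

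**The case against.** The case for leaving SAP 3.11 alone has real content. The section states no hypothesis, decision rule or claim, and SAP 3.12 reserves the 0.05 test for the primary endpoint. Listing all five classes may simply enumerate the scale; an empty class yields no estimate and so no bias or false positive. The interaction test is weak, so a non-significant result would not show that the effect is constant. A single pooled model also assumes a common variance that separate fits do not need, and SAP 3.9.1 log-transforms htTKV specifically because heterogeneity is expected.

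Most of this stands, and it limits the remedy: the joint model should be added with protection against unequal variances, not simply substituted for the class fits. It does not answer the central point. An ANCOVA repeated by class produces class-wise comparisons whether or not a claim is intended, and nothing in the SAP labels them exploratory or estimates the difference between classes.

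A reader might infer that chance positives are near certain, since 24 independent tests give 1 − 0.95²⁴ = 71%. The documents do not support that figure: the four visits use the same subjects. Treating them as one test gives 1 − 0.95⁶ = 26%, and even that takes htTKV and eGFR as independent. A reader might also infer that 1A and 1B must be strictly empty. They need not be, because entry uses local readings and the central reading may differ.

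**Conclusion.** The concern holds in a limited form. On the documents' own limits, classes 1A and 1B will be essentially empty, and the SAP contains no analysis of whether the effect depends on class. Under a uniform 57.2 mL effect, separate tests would give mixed significance about 68% of the time.

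That figure rests on an assumed 13 per arm in each class and on a t-test in mL with SD 90. The planned htTKV subgroup model is a baseline-adjusted ANCOVA on log10 values, so 34% and 68% indicate scale and are not the operating characteristics of that model. Nor would an interaction test settle the question at this sample size. Its value is that it addresses the right question and shows how uncertain the answer is. The primary analysis is untouched, and this is an inexpensive improvement to supportive output in a Phase 2b trial.

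**What to change.** In SAP 3.11:

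- Restrict modelling to classes 1C, 1D and 1E. Show any centrally read 1A or 1B subjects descriptively, or pool them with 1C. State which reading and which age assign the class.
- For each outcome and visit, add one ANCOVA on all subjects with treatment, class, treatment-by-class and the covariates already planned. Allow the residual variance to differ by class, or keep the per-class fits as a check on the pooled one.
- Report class-specific treatment effects with 95% confidence intervals, and the interaction estimate and test. Label all of it exploratory, and state that the interaction test has low power (about 11 to 51% under the splits and effect patterns above).

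The cost is SAP wording and a little more programming, with no new data. The joint model assumes common covariate slopes across classes and, if that option is taken, a common error variance.

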3.12 Multiplicity

The primary efficacy endpoint will be tested at the 2-sided 0.05 level. The secondary efficacy endpoints (ie, eGFR at months 12, 18, 24, and 30 days post-dose) will not be controlled for multiplicity for this Phase 2 study.

3.13 Safety Analysis

Safety assessments will include AEs, serious adverse events (SAEs), vital sign measurements, clinical laboratory evaluations (hematology and chemistry), and

electrocardiograms (ECGs). Unscheduled visits for safety assessments will not be presented in summary tables but will be in listings. All safety analyses will be performed using the Safety Population.

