Electrocardiograms will be performed with the subject in a supine position having rested in this position for at least 5 minutes before each reading. Triplicates should be obtained, with an interval of 1-2 minutes between ECGs.

During the study, all ECGs will be digitally analyzed by a validated central ECG vendor. Additional details on collection of ECGs will be provided in a separate manual.

The QT interval will be corrected using Fridericia's formula, adapted from Fridericia, 1920 12:

$$QT_F = \frac{QT}{RR^{1/3}}$$

All subjects must demonstrate an average screening QTcF value of \leq 450 msec by central digital analysis in order to be enrolled in the study. During the study, immediate clinical management of subjects will be based on results of machine-read ECGs at the sites. However, the central digital analysis will prevail as it becomes available. In addition, the central digital analysis will be used for any AE and SAE documentation.

An increase in QTcF interval (by central digital analysis) to a value > 60 msec above baseline or to the level of ≥ 480 msec requires further monitoring and, after collection of a PK blood sample and discussion with the Medical Monitor on appropriate management, the subject may be removed from the trial (see guidelines in Section 6.7.1.2).

Abnormalities in the ECG that lead to a change in subject management (eg, requirement for additional medication or monitoring) or result in clinical signs and symptoms are considered clinically significant for the purposes of this study and will be recorded on the AE eCRF. If ECG abnormalities meet criteria defining them as serious, they must be reported as an SAE (see Section 8.2.3).

Echocardiogram

Echocardiograms for determination of ejection fraction and evaluation of pericardial effusion and cardiac valve function will be collected at the time points specified in Table 2.

Ocular Monitoring

Ocular monitoring will be performed at the time points specified in Table 2. Ocular monitoring will include an assessment of best corrected distance visual acuity, fundoscopic exam with non-dilated pupils, slit lamp photography of the iris, non-mydriatic photography of retina within the arcade, and optical coherence tomography of the optic nerve head and macula.

Clinical Laboratory Evaluations

A central laboratory will perform clinical laboratory evaluations.

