3.13.1 Adverse Events

AEs will be coded using the MedDRA dictionary (Version 20.0). Treatment-emergent AEs (TEAEs) are any AE occurring or worsening in severity after the first administration of study medication. All AEs (including SAEs) will be graded using the 5-point Common Terminology Criteria for Adverse Events (CTCAE) V5.0 scale (mild, moderate, severe, life-threatening, or death). Causality with tesevatinib will be classified as: definitely related; probably related; possibly related; unlikely related; or not related. Definitely related, probably related and possibly related will be combined to related, unlikely related and not related will be combined to unrelated in some safety analyses.

The number and percentage of patients who experienced at least one TEAE as well as the number and percentage of patients who experienced AEs of each specific system organ class (SOC) and preferred term (PT) will be presented. For the presentation of AE incidences, the SOCs and the PTs within each SOC will be presented by decreasing total frequency. Tabulation by maximum severity and relationship to tesevatinib will also be included by treatment group.

The TEAEs, Grade \geq 3 TEAEs, SAEs, and TEAEs leading to dose modification/discontinuation will be summarized by treatment arm, SOC, and PT. These analyses will be repeated for events considered related (definitely related/probably related/possibly related) to tesevatinib.

Subject listings will be provided for SAEs, AEs resulting in study drug discontinuation, and deaths.

Adverse events will also be presented in listings. Time to onset and duration of AEs will be included in listings, along with action taken and outcome.

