3.13.2 Clinical Laboratory Evaluation

The summary statistics (including number, mean, standard deviation, median, minimum, and maximum) of all laboratory variables and changes from baseline will be calculated for each visit or study assessment by treatment group. For parameters of white blood cell counts, neutrophils (absolute count), lymphocytes (absolute count),

monocytes (absolute count), hemoglobin, platelets, ALP, ALT, aspartate aminotransaminase, gamma glutamyl transferase, total bilirubin, glomerular filtration rate, plots of mean/mean changes from baseline with the corresponding standard error will be displayed.

For shift tables, laboratory results will be classified using the common terminology criteria for adverse events (CTCAE) Version 5.0. All graded laboratory parameters will be summarized separately for hematology and biochemistry. Corresponding shift tables comparing baseline to the worst post-baseline grade within the treatment period will be provided.

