3.13.4 ECG

Descriptive statistics for ECG parameters (i.e., PR interval, QRS interval, and QTcF interval) at each time point with triplicate ECGs will be presented for the values and change from baseline scores. (QTcF is the QT interval using Fridericia's correction which is calculated by $QTcF = QT/(RR^{(1/3)})$.)

The number and percentage of subjects with observed QTcF values that satisfy the following conditions will be presented by treatment group and study visit and categorized as: ≤ 450 ms; > 450 to 480 ms; > 480 to 500 ms; and > 500 ms.

The number and percentage of subjects having change from baseline QTcF values that satisfy the following conditions will be presented by treatment group and study visit and categorized as: ≤ 0 ms; > 0 to ≤ 30 ms; > 30 to ≤ 60 ms; and > 60 ms.

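### The SAP text plans no count of subjects who ever reached the protocol's QTcF levels, and a crossing seen only on an off-schedule ECG enters no QTcF table

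*SAP*

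**What the plan says.** - **Unscheduled data.** SAP 3.13 gives one rule for all safety assessments, with no exception: "Unscheduled visits for safety assessments will not be presented in summary tables but will be in listings".
- **QTcF tables.** SAP 3.13.4: "The number and percentage of subjects with observed QTcF values that satisfy the following conditions will be presented by treatment group and study visit". Above the lowest category, the value bands are "> 450 to 480 ms; > 480 to 500 ms; and > 500 ms". The change-from-baseline bands, topped by > 60 ms, are also by treatment group and visit. No maximum or any-time row is described.
- **Protocol levels.** Protocol 7.5 (Electrocardiogram) says that a centrally read QTcF increase "to a value > 60 msec above baseline or to the level of ≥ 480 msec requires further monitoring".
- **Central reading.** The same section: "During the study, all ECGs will be digitally analyzed by a validated central ECG vendor".
- **Laboratory shift.** SAP 3.13.2: "Corresponding shift tables comparing baseline to the worst post-baseline grade within the treatment period will be provided". It does not mention unscheduled results.
- **Table shells.** SAP 4 places these in a separate document, so this point concerns the SAP text only.

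**The concern.** Safety and tolerability at 50 mg is a secondary objective. Protocol 1.2 reports that moderate QTc prolongation in 2 subjects at 100 mg led to the recommendation of 50 mg. A reader of the study report will want the matching figure here: how many subjects in each arm ever reached the protocol's QTcF levels. The protocol plans no Data Monitoring Committee (9.4) and performs its statistical analyses after lock and unblinding (9.3), so the final tables carry this comparison.

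Two features of the SAP text stand in the way. A by-visit count is not a count of subjects over the treatment period. And the blanket exclusion in 3.13 removes ECGs taken because something was suspected. Some of those are triggered by diarrhea, which the protocol expects as a class effect of EGFR inhibitors, so they could fall more often in the tesevatinib arm.

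**Working it through.** The plan states no figure to reproduce on this point. The check sets the sections side by side and uses small illustrations whose assumptions are marked.

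**1. Off-schedule ECGs are foreseen.** The protocol asks for an ECG on symptoms of arrhythmia (6.7, QT Interval Prolongation), with significant diarrhea (6.7, Diarrhea) and before restart after a hold for a QT-prolonging drug (5.2). All are centrally read (7.5). Under SAP 3.13 they go to listings. Both category tables in 3.13.4 are by visit, so these ECGs appear in neither.

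**2. Number of visit rows.** From protocol Table 2, footnotes b and f:
- Day 1 post-dose, Day 14 and Day 28: 3
- Months 2 to 12: 11
- Months 14 to 24, every second month: 6
- On-drug total: 3 + 11 + 6 = 20; with the End-of-study visit, 21

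Counting strict 28-day steps from day 56 to day 364 gives (364 − 56)/28 + 1 = 12 visits instead of 11, so each total rises by one. Nothing below depends on this.

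**3. Visit rows cannot be turned into subjects.** Assume 50 subjects in an arm, all attending.
- Case A: five subjects each cross a level once, at five different visits. Five rows show 1/50 = 2%. Ever crossed: 5/50 = 10%.
- Case B: one subject crosses at those same five visits. The same five rows show 1/50 = 2%. Ever crossed: 1/50 = 2%.

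The by-visit category counts are identical. With an assumed per-visit rate q over 21 visits, two reference patterns (not bounds) are: the same subjects cross every time, so the ever-crossed share is q; or visits are independent, so it is 1 − (1 − q)^21.

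| Assumed q | Same subjects each visit | Independent visits |
|---|---|---|
| 0.5% | 0.5% | 10.0% |
| 1% | 1% | 19.0% |
| 2% | 2% | 34.6% |

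**4. Effect of dropping off-schedule ECGs.** Assume five subjects in an arm truly cross. If 25% or 50% of them cross only on an off-schedule ECG, scheduled data account on average for 5 × 0.75 = 3.75 or 5 × 0.50 = 2.5 of them. The documents give no basis for choosing a share.

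**5. Band edge.** A value of exactly 480 meets the protocol's ≥ 480 level but falls in the SAP's lower band. Adding the two top bands at a visit gives subjects above 480, not at or above it. The > 60 ms change band does match the protocol cut-point.

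**6. Reference value for change.** Protocol 6.7.1.2 compares with the highest average predose value, then describes it as the average of Day 1 predose and screening. SAP 3.2.3 uses the last valid value in the 28 days before first dose unless the assessment's section says otherwise, and 3.13.4 says nothing. Assumed example: screening 420, Day 1 predose 400, maximum 465 msec.
- SAP last value: 465 − 400 = 65, which is > 60
- Higher of the two predose values: 465 − 420 = 45, not > 60
- Average of the two: 465 − 410 = 55, not > 60

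The same subject is counted or not counted depending on the reference.

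**The case against.** **The SAP follows the protocol, and other outputs exist.** Protocol 9.11 itself plans ECG summaries by group and visit. SAP 3.13.4, with the descriptive statistics defined in SAP 3.2.1.1, tabulates each arm's maximum QTcF and maximum change at every visit. A crossing requires monitoring, so under protocol 7.5 it should be recorded as an adverse event. SAP 3.13.1 counts those by preferred term and adds: "Tabulation by maximum severity and relationship to tesevatinib will also be included by treatment group". Listings hold every value, and protocol 9.11 promises that important findings will be summarized or listed.

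All of this is true, and it rules out any reading that QTcF crossings are hidden or lost. None of it supplies the missing count. A per-visit maximum shows whether someone crossed at that visit, not how many subjects ever did. Adverse event tables count reported terms. The protocol has severity graded by symptoms and activity (Table 7) while SAP 3.13.1 names CTCAE V5.0, and the documents do not show that either grade fixes a msec level. The promise about important findings is met by a listing alone. The separate shells may already contain such a row, but the SAP text does not require it.

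**A reader might infer that the laboratory shift tables lose worst grades.** The documents do not support that. SAP 3.13.2 sets its own scope, the worst grade within the treatment period, and is most naturally read as covering every result. A shift table has no visit rows, so the 3.13 rule is plausibly aimed elsewhere. The amylase sequence in protocol 6.7 does involve an off-schedule draw, but it starts from a value already > 2.0 × ULN. The later re-test changes the worst grade only if it exceeds the grade of that trigger, and the SAP does not say that amylase is a graded parameter. Locally run panels are outside the final analysis (protocol 7.5). What remains is a clarifying clause.

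**More testing means more chances of an extreme value.** A maximum over all ECGs can be inflated in the arm tested more often. This stands, and it is a reason to keep the scheduled-visit tables beside the new one.

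**Conclusion.** The point holds for QTcF. As the SAP text stands, a crossing seen only on an off-schedule ECG enters no QTcF table, and no described table gives the number of subjects per arm who ever reached > 60 msec above baseline or ≥ 480 msec. For laboratory data it comes down to one clause on scope.

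The size cannot be stated in subjects: the documents give neither a crossing rate nor a rate of off-schedule ECGs, and every percentage above is an assumed illustration. No primary result, alpha or power is affected, and no data are lost. This is a cheap improvement to safety reporting, not a flaw in the design. It assumes that the separate shells do not already contain a maximum-value table.

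**What to change.** 1. In SAP 3.13, limit the exclusion of unscheduled assessments to by-visit descriptive tables. In 3.13.2, add one clause confirming that the worst-grade shift uses all on-treatment central-laboratory results, scheduled or not.
2. In SAP 3.13.4, add one table by arm of each subject's maximum on-treatment QTcF and maximum change from baseline, from all centrally read ECGs, with a cut-point that counts ≥ 480 msec. Define on-treatment so that it is clear whether ECGs taken during a hold, such as the pre-restart ECG, are included.
3. State in 3.13.4 which baseline the change uses, and reconcile protocol 6.7.1.2 with SAP 3.2.3.
4. Footnote the new table to say that subjects tested more often have more chances of an extreme value, and keep the scheduled-visit tables alongside.

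The cost is a few sentences of SAP wording, one table shell with its footnote, and the baseline reconciliation, which touches protocol text. The ECG data are already to be collected and centrally read. The wording should be settled before unblinding, when protocol 9.3 requires the SAP to be final.
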